### **13.8 12-Lead Electrocardiogram Measurements**

Single 12-lead ECGs will be measured after the subject has been in the supine position for a minimum of 5 minutes, and triplicate 12-lead ECG measurements will be performed approximately 2 min apart after the subject has been in the supine position for a minimum of 5 min, according to the Schedule of Assessments presented in [Appendix 2](#) (Part 1) and [Appendix 3](#) (Part 2). The acceptable deviations from the nominal ECG assessment times are detailed in the schedules.

If a subject shows an abnormal assessment at any stage repeat measurements may be made and the abnormality followed to resolution if required. Additional measurements may be taken as deemed necessary by the investigator or sub-investigator.

Any clinically significant abnormality, including changes from baseline, will be reported as an AE.

### **13.9 Body Weight, Height and Body Mass Index**

The subject's body weight and height will be measured and their BMI calculated according to the Schedule of Assessments presented in [Appendix 2](#) (Part 1) and [Appendix 3](#) (Part 2).

### **13.10 Physical Examination**

Subjects will undergo a physical examination according to the Schedule of Assessments presented in [Appendix 2](#) (Part 1) and [Appendix 3](#) (Part 2).

### **13.11 Additional Safety Procedures**

Additional non-invasive procedures that are already specified in the protocol may be performed if it is believed that an important effect of the IMP is occurring, may occur at a time when no measurements are scheduled or if extra procedures are needed in the interests of safety.

Additional blood samples, urine samples or other diagnostic tests for safety assessments may be taken if required by the investigator or sub-investigator at any point.

## **14 Statistics and Data Analysis**

### **14.1 Sample Size Justification**

Based on experience from previous similar studies, the target numbers of subjects to be enrolled (N = 8 and N = 12) should be sufficient to achieve a minimum of 6 and 8 evaluable subjects in each cohort in Part 1 and Part 2, respectively. Six evaluable subjects in SAD is customarily sufficient to assess cohorts for dose escalation. The sample size of 12 in MAD is supported by results of daily sargramostim (6 mcg/kg/day) for 8 weeks administered to 20 persons with Parkinson's Disease in a randomized (1:1), placebo-controlled trial (Gendelman 2017). A significant transient increase of 5% CD4+Treg counts (Mann-Whitney U test p=0.05-0.01) and Treg activity was identified at 2-4 weeks with data from 5-9 sargramostim treated patients). GM-CSF at a dose of 5-10 mcg/kg/day for 4-5 days significantly increased numerous cell lineages in peripheral blood of 5-8 healthy volunteers, with increases in CD34+ mononuclear cells, WBC, MNC, PMN, monocytes, and eosinophils (Lane 1995; Fishmeister 1999). PD patients also have increases in PMN and eosinophils in response to sargramostim (Gendelman 2017). These results suggest the MAD sample size is sufficient to detect an increase of 5% in mean Treg percentages compared with pooled placebo subjects. The sample size is also adequate to identify expected pharmacodynamic changes in hematology laboratory tests.

### **14.2 Data Management**

Data management will be performed by Quotient.

Study data will be managed using a validated eCRF database system and subjected to data consistency and validation checks. Data queries will be raised within the study eCRF

database by data management staff and resolved with the assistance of clinical staff. The database is compliant with 21 Code of Federal Regulations (CFR) Part 11 guidelines.

AEs, medical histories and medications will be coded using the Medical Dictionary for Regulatory Activities (MedDRA) (version to be specified in the Data Management Plan [DMP]) and the World Health Organization (WHO) Drug Dictionary Global Drug Reference (version to be specified in the DMP), respectively. An independent coding review will also be performed within the Data Sciences department.

Clinical chemistry and hematology data (and other safety laboratory data) will be collected by Quotient Labs and Quest Diagnostics Clinical Laboratories Inc and stored electronically in their laboratory information system. The data will be transferred electronically to Quotient and all demographic details and sample dates will be cross-referenced with the corresponding data on the study database. All queries will be resolved with the assistance of laboratory staff, or if necessary, clinical staff.

The database will be closed after all queries have been resolved. The database will be locked when all criteria listed in the DMP are met.

Further details are addressed in the DMP.

#### **14.3 Pharmacokinetic Data Analysis**

The PK data for PDM608 will be analyzed by Quotient, using Phoenix WinNonlin v8.0 or a more recent version (Certara USA, Inc., USA).

PK analysis of the concentration time data obtained will be performed using appropriate non-compartmental techniques to obtain estimates of the PK parameters presented in Table 4, where possible and appropriate.

**Table 4 Pharmacokinetic Parameters**

Parameter	Definition
Part 1 SAD	
$t_{max}$	Time of maximum observed concentration
$C_{max}$	Maximum observed concentration
$C_{max}/Dose$	Maximum observed concentration divided by dose
$AUC_{(0-24)}$	Area under the curve from time 0 to 24 hr
$AUC_{(0-last)}$	Area under the curve from time 0 to the time of last measurable concentration
$AUC_{(0-last)}/Dose$	Area under the curve from time 0 to the time of last measurable concentration divided by dose
$AUC_{(0-inf)}$	Area under the curve from time 0 extrapolated to infinity
$AUC_{(0-inf)}/Dose$	Area under the curve from time 0 extrapolated to infinity divided by dose
$AUC_{extrap}$	Area under the curve from time of the last measurable concentration to infinity as a percentage of the area under the curve extrapolated to infinity

Parameter	Definition
$T_{1/2}$	Terminal elimination half-life
Lambda-z	First order rate constant associated with the terminal (log-linear) portion of the curve
CL/F	Total body clearance calculated after extravascular administration where F (fraction of dose bioavailable) is unknown
Vz/F	Apparent volume of distribution based on the terminal phase calculated using $AUC_{(0-\infty)}$ after a single extravascular administration where F (fraction of dose bioavailable) is unknown

**Part 2 MAD – Dose 1, Dose 2, and Dose 3**

$T_{max}$	Time of maximum observed concentration
$C_{max}$	Maximum observed concentration
$AUC_{(0-24)}$	Area under the curve from time 0 to 24 hr
$AUC_{(\tau)}$	Area under the curve for the defined interval between doses ( $\tau$ )

**Part 2 MAD – Dose 4**

$t_{max}$	Time of maximum observed concentration
$C_{max}$	Maximum observed concentration
$AUC_{(0-24)}$	Area under the curve from time 0 to 24 hr
$AUC_{(\tau)}$	Area under the curve for the defined interval between doses ( $\tau$ )
$T_{1/2}$	Terminal elimination half-life
Lambda-z	First order rate constant associated with the terminal (log-linear) portion of the curve
AR $C_{max}^*$	Accumulation Ratio based on $C_{max}$ last dose / $C_{max}$ first dose
AR $AUC^*$	Accumulation Ratio based on $AUC_{(0-\tau)}$ last dose / $AUC_{(0-\tau)}$ first dose
$Vz/F$	Apparent volume of distribution based on the terminal phase after extravascular administration where F (fraction of dose bioavailable) is unknown

\*These parameters will not be calculated if Dose 1 is a loading dose.

Further details of the PK data analysis will be included in the Reporting and Analysis Plan (RAP).

#### 14.4 Statistical Data Analysis

Statistical analysis and production of summary tables, figures and listings for this study will be performed by Quotient using the statistical package SAS (v9.4 or more recent version).

In general terms, categorical data (including treatment-emergent AEs) will be presented using counts and percentages, while continuous variables will be presented using the mean, median, standard deviation, minimum and maximum. Additional statistics will be provided for PK-related data including coefficient of variation (CV%), geometric mean and geometric CV%.

Descriptive summaries for all safety data (AEs, vital signs, ECGs and safety laboratory assessments) by treatment will be provided (including changes from baseline as required).

Descriptive summaries for all PK and PD data by treatment will be provided, including changes from baseline in PD variables. The number and percentage of subjects with confirmed ADA response will be presented, both prevalence and incidence.

All safety, PK and PD data will be listed.

The following formal statistical analysis may be performed:

Dose proportionality for SC doses - assessed using a power model using log-transformed  $AUC_{(0-\text{last})}$ ,  $AUC_{(0-\text{inf})}$  (Part 1), and  $AUC_{(0-\tau)}$  (Part 2) and  $C_{\max}$  values (e.g., a linear model with log dose as a covariate). The resulting estimated slope (b) is a measure of dose proportionality (e.g., the relationship is dose proportional when b=1). Dose proportionality will be assessed on each of Day 1/Dose 1 (SAD and MAD) and Dose 4 (MAD only).

Accumulation - assessed in Part 2 on log-transformed parameters  $AUC_{(0-\tau)}$  and  $C_{\max}$  values using a mixed effects model with terms for treatment (e.g., dose level) and day as fixed effects, a day by treatment interaction term and subject as a random effect. Ratios of geometric means and 90% CI will be provided for Dose 2/3/4 versus Dose 1. Accumulation ratios will not be calculated if Dose 1 is a loading dose.

Pharmacodynamics – Leukocyte numbers/percentages and Treg numbers/percentages will be compared between the active treatment and placebo groups using t-tests. Non-parametric statistics may be used for comparison if the data distribution suggest they are more appropriate. Changes from baseline in both groups will be summarized descriptively. Specific PK/PD modelling (e.g., Emax model fit) may be performed.

Populations and analysis sets will be determined for safety, PK, ADA and PD (if applicable) after database lock using the criteria defined in the RAP; the RAP will be signed off prior to database lock.

The safety and PD populations and analysis sets will be defined after database lock but prior to study unblinding; all other populations will be defined after database lock when the relevant data are available.

Further details relating to the statistical analysis will be included in the RAP including the following:

- Criteria to be used to define each of the population and analysis sets
- Additional detail covering the analyses and/or description of primary and secondary analyses and safety data
- Handling of missing data, unused or spurious data
- Handling of data from withdrawn subjects

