The maximum PDM608 dose administered in either part of this trial will not exceed a dose that is more than two-fold above the dose at which any two of the following three pharmacodynamic activities are observed in a sample that includes a minimum 5 of 6 PDM608-treated subjects in SAD or 7 of 9 PDM608-treated subjects in MAD, treated within the same cohort, and observed at any laboratory timepoint up to and including 96 hours post-dose (SAD) and post-final dose (MAD):

- An increase in mean WBC from pre-dose baseline by  $\geq$  3-fold
- An increase in mean monocytes from pre-dose baseline by  $\geq$  2-fold
- An increase in mean eosinophils from pre-dose baseline by  $\geq$  7-fold

The above three hematologic parameters will be described and made available for review by the SAC when making dose level decisions.

Intra-subject changes are considered because of the wide-variability of hematological parameters between subjects, and because smaller numbers of subjects are allocated to placebo treatment. Multiple pharmacodynamic endpoints are selected to minimize the impact of outliers on mean values. A statistical test is not applied to these pharmacodynamic effects. Dose escalation beyond this point (as described above) is permitted in order to obtain pharmacokinetic and pharmacodynamic margin for subsequent patient studies. This pharmacodynamic limit assumes that PDM608 remains safe as defined by the other stopping rules in [Section 8.5](#).

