## 7 Objectives and Endpoints

Objectives	Endpoints
Primary	
To assess the safety, tolerability and PK of single (Part 1) and multiple (Part 2) SC doses of PDM608	
 
Incidence of AEs, change from baseline for physical examinations and vital signs, electrocardiograms (ECGs) and laboratory safety tests including ADA in blood
 
PK parameters for PDM608
 

Secondary	
To assess immunogenicity following single and multiple doses of PDM608	Incidence of ADA in blood
Exploratorya	
To assess PD following administration of single (Part 1) and multiple (Part 2) ascending SC doses of PDM608	
 
Individual baseline corrected leukocyte, Treg and other immune cell numbers/percentages
 
Individual baseline corrected cytokine levels
 

a Exploratory PD biomarker objectives may be reported separately to the Clinical Study Report.

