- Upon the subject's request (withdrawal of consent)
- Significant deviation from the protocol, as determined by the Investigator and Sponsor
- Significant concurrent illness or requirement for prohibited medication

- Subject non-compliance
- At the discretion of the investigator

Baseline will be considered the last available assessment prior to first dose for the purpose of withdrawal criteria.

Every effort will be made to ensure that subjects who discontinue IMP administration because of an IMP-related AE will complete all safety follow-up procedures.

Early withdrawal for any of the above reasons should be documented and distinguished from withdrawal of consent by the subject to participate in any further activities.

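### The optional t-test of Treg and leukocyte values has no baseline term and does not clearly match the baseline-corrected endpoint; ANCOVA on the pre-dose value would be a cheap, conditional gain in precision

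*Combined protocol and SAP*

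**What the plan says.** Section 14.4, in its pharmacodynamics paragraph, states: "Leukocyte numbers/percentages and Treg numbers/percentages will be compared between the active treatment and placebo groups using t-tests". A non-parametric test is the fallback if the distribution calls for it. The paragraph then adds: "Changes from baseline in both groups will be summarized descriptively". It does not say whether post-dose values or changes are tested, at which visit, or whether placebo is pooled across cohorts. The whole list of formal analyses is introduced as optional, whereas the Synopsis presents these analyses as ones that will be done.

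Two other places point to a baseline-corrected outcome. Section 7 gives the exploratory endpoint as "Individual baseline corrected leukocyte, Treg and other immune cell numbers/percentages", with the footnote "Exploratory PD biomarker objectives may be reported separately to the Clinical Study Report". The Synopsis (Statistical Methodology) describes the formal Treg analysis as an assessment of changes in cell numbers.

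The only explicit definition of baseline is in Section 8.3 and has a restricted purpose: "Baseline will be considered the last available assessment prior to first dose for the purpose of withdrawal criteria". Section 14.1 asserts that "the MAD sample size is sufficient to detect an increase of 5% in mean Treg percentages compared with pooled placebo subjects". Section 14.4 defers further detail to the RAP, and "the RAP will be signed off prior to database lock".

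**The concern.** Taken alone, Section 14.4 suggests that the formal test uses post-dose values, because changes are assigned to description. Section 7 and the Synopsis suggest that it uses changes. These are different tests with different power, and a reader cannot tell which will be run.

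Neither uses the subject's own pre-dose value as a covariate. The protocol gives a reason to do so when it explains the hematology dose cap in Section 6.4: "Intra-subject changes are considered because of the wide-variability of hematological parameters between subjects". That section adds that few subjects receive placebo. Both reasons apply equally to the comparison in Section 14.4.

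The data are already planned. Appendices 2 and 3 show a PD sample before dosing on Day 1 and a hematology sample on Day -1 in both Parts. What is at stake is the width of the intervals in the formal comparison that corresponds to the Treg statement in Section 14.1.

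**Working it through.** **The plan's own figure.** The Section 14.1 statement cannot be reproduced, because no SD, alpha or power is given for this trial. If 5% is read as percentage points, with two-sided 0.05, 80% power and 9 against 9, the t-test needs a standardised difference of 1.407. The SD could then be at most 5 / 1.407 = 3.55 points. The documents do not allow a check of whether it is.

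**Inputs from the documents.** Part 2: 9 active and 3 placebo per cohort, so pooled placebo is 3 × 3 = 9 (or 4 × 3 = 12 with the optional cohort). Part 1: 6 active and 2 placebo per cohort, so pooled placebo is 5 × 2 = 10. The Section 8.2.2 minimum for Part 2 escalation is 8 completers with at least 6 active; 6 active and 2 placebo over three cohorts gives 6 against 6.

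**Assumptions, not from the documents.** Two-sided 0.05; normal data; equal variance in the two arms; rho from 0 to 0.9; an effect of d = 0.97 post-dose SDs for the power figures. The interval widths do not depend on d.

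**Formulas.** Set the post-dose SD to 1, the baseline SD to s, the total number to N, and k = 1 + 1/(N − 4).
- Variance: post-dose 1; change 1 + s² − 2·rho·s; ANCOVA (1 − rho²)·k.
- Degrees of freedom: N − 2 for the t-tests, N − 3 for ANCOVA.
- Width of the ANCOVA 95% interval relative to post-dose: sqrt((1 − rho²)·k) × t(0.975, N − 3) / t(0.975, N − 2).
- Power: noncentral t with noncentrality d / sqrt(variance × (1/n1 + 1/n2)).

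**Example, 9 against 9, rho 0.5.** k = 1 + 1/14 = 1.071. ANCOVA variance = 0.75 × 1.071 = 0.804. Width ratio = 0.896 × 2.131 / 2.120 = 0.90. Noncentrality = 0.97 / sqrt(0.804 × 2/9) = 2.30, giving 57% power on 15 degrees of freedom.

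**Results, 9 against 9:**

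| rho | ANCOVA width vs post-dose | ANCOVA power | Post-dose power | Change power, s = 1 | Change power, s = 0.5 |
|---|---|---|---|---|---|
| 0 | 1.04 | 46% | 49% | 28% | 41% |
| 0.3 | 0.99 | 50% | 49% | 37% | 51% |
| 0.5 | 0.90 | 57% | 49% | 49% | 61% |
| 0.7 | 0.74 | 74% | 49% | 70% | 74% |
| 0.8 | 0.62 | 87% | 49% | 86% | 82% |
| 0.9 | 0.45 | 99% | 49% | 99% | 90% |

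**Part 1, 6 against 10, same rho values, s = 1.** ANCOVA 39/42/49/65/79/97%; post-dose 42% throughout; change 24/32/42/62/79/97%.

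**Break-even on variance.** ANCOVA beats post-dose if rho exceeds sqrt(1 − 1/k): 0.26 for 9 against 9, 0.28 for 6 against 10, 0.33 for 6 against 6 or 9 against 3. With s = 1 it beats the change score if rho is below 2/k − 1: 0.87, 0.85 and 0.78 respectively.

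**Where ANCOVA loses.**
- Against post-dose at rho 0: 49% to 46% (9 against 9) and 42% to 39% (6 against 10). From an 80% base, 6 against 6 or 9 against 3 falls to 74%.
- Against change with s = 0.5 and rho 0.5: 57.4% against 60.7% (9 against 9) and 48.8% against 52.4% (6 against 10). For 6 against 6 or 9 against 3 the loss is about 4 to 5 points.

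**Unequal variances.** In a simulation at rho 0.6 with 6 against 10 and an active SD 2 or 3 times the placebo SD, nominal 95% ANCOVA intervals cover about 90% and 88%. Pooled-variance t intervals do no better (90% and 87%); Welch intervals stay near 95%.

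**The case against.** The strongest reply is that nothing here is an error. The endpoint is exploratory and may be reported outside the CSR, and the test is optional. Both forms of t-test are legitimate in a randomised comparison, and the RAP is still to come. This stands, and it sets the severity.

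A second reply is that Section 7 and the Synopsis together make a change-score test the likelier intention, and wide between-subject variability suggests a high rho, where ANCOVA adds little to a change score. This stands in part. At rho 0.7 to 0.9 with equal SDs the difference is 4 points or less. But rho is unknown, and each t-test loses heavily if it is the wrong one: the change score at low rho, the post-dose test at high rho. With equal SDs, ANCOVA for 9 against 9 stays within about 3 points of the better of the two throughout.

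Third, leukocyte spread may grow with treatment: Section 6.4 cites rises of more than 3-fold in WBC and 7-fold in eosinophils. That is a fair caution against plain ANCOVA on raw counts, and the remedy has to allow for it.

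The RAP deferral does not dispose of the point. The t-test is the method the protocol states, and the listed RAP contents mention primary, secondary and safety analyses without naming exploratory PD, although the list is not exhaustive.

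A reader might infer that the planned test is biased, that the trial ignores baseline, or that the Section 14.1 claim fails. The documents support none of these. Randomisation protects both forms of the comparison, Section 7 and the Synopsis refer to baseline correction or change, and without an SD the Section 14.1 claim can be neither confirmed nor refuted.

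**Conclusion.** The point holds as a low-severity matter of clarity and precision. Section 14.4 should be reconciled with Section 7 and the Synopsis on what is tested, and a covariate that is already collected goes unused. No escalation rule in Section 8.2.2 uses this test, and the primary objective does not rest on it.

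The gain is conditional. It is material against a post-dose test once rho reaches about 0.5, material against an equal-SD change score only at low to moderate rho, and absent against that score at 0.9. It turns into a small loss when rho is near 0, or when the baseline SD is about half the post-dose SD and rho is about 0.5. It would therefore be too strong to say that ANCOVA is always better. All power figures rest on the assumed d, alpha, rho, SD ratio and equal arm variances. Pooling of placebo is taken from Section 14.1, because Section 14.4 is silent on it.

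**What to change.** In Section 14.4, or in the RAP before sign-off:

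- Name the PD visit, and compare each dose group with placebo pooled within Part by ANCOVA, with the pre-dose value as covariate.
- Define the baseline: the Day 1 pre-dose PD sample for flow cytometry and the Day -1 sample for hematology counts.
- Use the log scale or a variance-robust method for leukocyte counts.
- Report adjusted differences or ratios with confidence intervals, and keep the t-test or non-parametric test as a sensitivity analysis.
- If a t-test stays as the main test, run it on change from baseline, so that it agrees with Section 7 and the Synopsis.

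This is wording only, with no new samples or visits. The statistical cost is one degree of freedom, plus the small power losses shown above in the unfavourable settings.

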### 6.4 Pharmacodynamic Rationale

GM-CSF is approved for peripheral blood mobilization of CD34+ stem cells for transplantation. The approved dose of sargramostim for autologous mobilization is 250 mcg/m^2/day SC (6-7 mcg/kg) which greatly increases precursor cell frequencies. For allogeneic transplant, donors are often prepared with four daily doses of GM-CSF followed by apheresis.

One goal of the PDM608 early development program is to identify a safe, tolerated dose of PDM608 that increases peripheral blood Tregs, which can be profiled in neurodegenerative diseases, such as Parkinson's disease. Short-acting GM-CSF appears to increase various cell lineages with roughly similar kinetics, with the degree of change dependent on the cell type. We will take advantage of the known pharmacodynamic effects of GM-CSF to inform dose escalation decisions.

GM-CSF at a dose of 5-10 mcg/kg/day for 4-5 days increased numerous cell lineages in peripheral blood of healthy volunteers, with increases in WBC, MNC, PMN, monocytes,

and eosinophils (Lane 1995; Fishmeister 1999): WBC increased greater than 3-fold, MNC and monocytes increased greater than 2-fold and eosinophils increased greater than 7-fold. The time course of Treg elevation in humans is not well-known, but was increased two-fold after 2 weeks daily exposure to GM-CSF in persons with Parkinson's disease (Gendelman 2017). A preclinical PKPD study with PDM608 demonstrated dose-dependent elevation of Regulatory Helper T cells and Regulatory Cytotoxic T Cells in cynomolgus monkey 10 days after weekly dosing (CBR-PDM608-110).

An increase of 5% in mean Treg percentages compared with pooled placebo subjects may be considered a meaningful treatment effect for future patient studies ([Section 14.1](#)), thus dose escalation will be optimized through analysis of Tregs as a pharmacodynamic parameter.

Pharmacodynamic analysis may include immunophenotyping by flow cytometry to determine numbers/percentages of certain immune cells, and cytokine analysis ([Section 12](#)), as well as analysis of a subset of the safety hematology labs (WBC, monocyte, and eosinophil values) as an indicator of pharmacodynamic activity.

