#### 8.1.1 Study Plan: Part 1 Single Ascending Doses

Part 1 is a double-blind, randomized, placebo-controlled assessment of SC PDM608 SAD administrations. Subjects will be enrolled sequentially into 1 of up to 5 cohorts, each containing 8 subjects. Within each cohort, 6 subjects will be randomly assigned to receive PDM608 and 2 subjects will be randomly assigned to receive matching placebo. An evaluable subject for Part 1 is defined as a subject who has received the IMP dose and undergone all safety and tolerability assessments (inclusive of all scheduled hematology assessments) out to 96 hours post.

All SAD Cohorts will follow a sentinel design. On the first day of dosing only 2 (sentinel) subjects will be dosed. The randomization schedule will be constructed such that 1 of the subjects dosed on the first day will receive PDM608 and 1 will receive placebo. After review of the safety data from the 72 hours post-dose period the Investigator will decide whether to proceed with dosing the remaining subjects in the cohort (main group; 5 subjects randomized to receive PDM608 and 1 subject randomized to receive placebo).

Following completion of each cohort the safety and tolerability assessments through 96 hours post-dose (Day 5) will be reviewed by the SAC to determine whether to progress to the next dose level and the dose level for the next cohort, with a maximum 3-fold increase in dose level between SAD cohorts.

Following dosing of at least 3 SAD cohorts, the SAC will also decide whether to progress to MAD Part 2 of the study and, if so, on the starting dose for the first MAD cohort. Part 2 may be dosed in parallel with Part 1, but the decision to proceed to Part 2 can only be made following interim review of safety and tolerability data from doses through SAD Cohort 3. Full details of the interim data reviews are provided in [Section 8.2](#).

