**Figure 1 Study Sequence: Part 1 Single Ascending Doses****8.1.2 Study Plan: Part 2 Multiple Ascending Doses**

Part 2 is a double-blind, randomized, placebo-controlled assessment of SC PDM608 MAD administrations. Subjects will be enrolled sequentially into 1 of up to 4 cohorts, each containing 12 subjects. Within each cohort, 9 subjects will be randomly assigned to receive PDM608 and 3 subjects will be randomly assigned to receive matching placebo. MAD Cohort 4 is optional; the decision on whether to dose this cohort will be based on interim review of preceding MAD Cohorts 1 to 3.

Part 2 may be dosed in parallel with Part 1, but can only proceed following interim review of safety and tolerability data from at least the first 3 SAD cohorts in Part 1. Dosing for each MAD cohort will be at a dose level 2-3 fold lower than the highest SAD cohort dose deemed safe by the SAC at the time of each MAD cohort initiation.

An evaluable subject for Part 2 is defined as a subject who has received all 4 doses of IMP and undergone all safety and tolerability assessments out to 96 hours post-final dose (dose 4). Sentinel dosing is not planned for MAD cohorts, but the SAC may implement a sentinel design if deemed appropriate.

Following completion of each cohort, the safety and tolerability assessments out to 96 hours post-final dose (Day 26) will be reviewed to determine whether to progress to the next dose level and the dose to be administered. Full details of the interim data reviews are provided in [Section 8.2](#).

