## 8.8 Subject Selection List and Randomization

This is a double-blind, randomized, placebo-controlled study; therefore, a randomization schedule will be produced for each study part.

A subject selection list will be produced for each study part prior to dosing using the randomization schedule and will be retained in the Investigative Site File (ISF).

In Part 1, for sentinel dosing, a group of 2 subjects will be dosed ahead of the remaining subjects in each cohort. A randomization schedule will be used such that the first 2 subject numbers will be allocated to active or placebo in a 1:1 ratio (i.e., 1 subject will be randomly assigned to receive PDM608 and 1 subject will be randomly assigned to receive matching placebo). The remaining 6 subject numbers will be allocated to active or placebo in a 5:1 ratio (i.e., 5 subjects will be randomly assigned to receive PDM608 and 1 subject will be randomly assigned to receive matching placebo).

For Part 2, a randomization schedule will be used to allocate subject numbers to PDM608 or placebo in a 3:1 ratio (i.e., in each cohort, 9 subjects will be randomly assigned to receive PDM608 and 3 subjects will be randomly assigned to receive matching placebo).

Subjects will be randomized prior to administration of the first dose.

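### The active-versus-placebo t-tests on Treg and leukocyte values leave out cohort, the unit within which subjects are randomized

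*Combined protocol and SAP*

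**What the plan says.** The pharmacodynamic paragraph of Section 14.4 reads: "Leukocyte numbers/percentages and Treg numbers/percentages will be compared between the active treatment and placebo groups using t-tests". It allows a non-parametric alternative and keeps changes from baseline descriptive. It names no cohort, stratum or covariate. It also does not say whether the active group means one dose cohort or all active subjects.

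The comparator is described elsewhere. Section 6.4: "An increase of 5% in mean Treg percentages compared with pooled placebo subjects may be considered a meaningful treatment effect". Section 14.1, after defending the Part 2 cohort size of 12: "These results suggest the MAD sample size is sufficient to detect an increase of 5% in mean Treg percentages compared with pooled placebo subjects".

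On design, Section 8.1.1 says of Part 1: "Subjects will be enrolled sequentially into 1 of up to 5 cohorts, each containing 8 subjects", and "Within each cohort, 6 subjects will be randomly assigned to receive PDM608 and 2 subjects will be randomly assigned to receive matching placebo". Section 8.1.2 says of Part 2: "Subjects will be enrolled sequentially into 1 of up to 4 cohorts, each containing 12 subjects". Section 8.8 gives the Part 2 allocation: "in each cohort, 9 subjects will be randomly assigned to receive PDM608 and 3 subjects will be randomly assigned to receive matching placebo". Each cohort has one active dose level, and Cohort 4 of Part 2 is optional.

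Section 7 lists the pharmacodynamic objective as exploratory, with baseline-corrected endpoints. Section 14.4 leaves further statistical detail to the Reporting and Analysis Plan (RAP), which is not among the documents.

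**The concern.** The trial creates its placebo comparison separately within each cohort, and the cohorts run one after another. A two-sample t-test ignores that structure. What follows depends on which comparison is meant.

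- **All active against all placebo.** Any variation between cohorts enters the error term, although the constant allocation ratio has already balanced it out of the treatment difference. Power is lost for no return.
- **One cohort's active subjects against pooled placebo.** Most of the controls were randomized in other cohorts at other times. With four Part 2 cohorts, 9 of 12 placebo subjects are non-concurrent; with five Part 1 cohorts, 8 of 10 are. A difference between cohorts can then be read as a drug effect.

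At stake is the reading of the Treg result, which Section 6.4 ties to a meaningful effect for later patient studies.

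**Working it through.** **Plan's own figure.** Section 14.1 gives no SD, alpha or power for the 5% Treg increase, so there is nothing to reproduce. The check below is in units of the within-cohort SD.

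**Inputs.** From the documents: K = 4 or 3 cohorts of 9:3 (Part 2) and K = 5 cohorts of 6:2 (Part 1). Assumed: two-sided alpha 0.05, within-cohort SD 1, between-cohort SD τ of 0, 0.25, 1/3 or 0.5, and an effect of 0.9 SD for power. As a share of total variance, τ²/(1+τ²), these values of τ are 0%, 6%, 10% and 20%.

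**Step 1: all active against all placebo, Part 2, four cohorts (36 v 12).** Each cohort makes up 1/4 of both group means, so cohort shifts cancel from the difference.

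- True variance of the difference: 1/36 + 1/12 = 0.111. Noncentrality: 0.9/√0.111 = 2.70.
- Expected t-test error variance: 1 + τ²[(36−9) + (12−3)]/46 = 1 + 0.783τ². This overstates the true value, so the critical value 2.013 (46 df) acts as 2.013 × √(1 + 0.783τ²).
- With cohort as a fixed factor there are 48 − 1 − 4 = 43 df, the critical value is 2.017, and τ drops out.

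| τ | effective critical value | rejection with no drug effect | power, t-test | power, cohort term |
|---|---|---|---|---|
| 0 | 2.013 | 5.0% | 75% | 75% |
| 1/3 | 2.099 | 4.1% | 73% | 75% |
| 0.5 | 2.201 | 3.3% | 69% | 75% |

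**Step 2: one cohort's active subjects against pooled placebo, no drug effect.** The cohort effects no longer cancel.

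- True variance: 1/a + 1/(Kp) + τ²(1 − 1/K), where a and p are the active and placebo numbers per cohort.
- Expected variance used by the t-test: [1 + τ²(Kp − p)/(a + Kp − 2)] × [1/a + 1/(Kp)].

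For four Part 2 cohorts at τ = 0.5:

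- True: 0.1944 + 0.25 × 0.75 = 0.3819.
- Used: (1 + 0.25 × 9/19) × 0.1944 = 0.2175.
- Ratio 1.756, so the critical value 2.093 (19 df) acts as 2.093/√1.756 = 1.58, and the rejection rate is 13.1%.

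| Setting | τ = 0 | τ = 0.25 | τ = 0.5 |
|---|---|---|---|
| Part 2, 4 cohorts (9 v 12) | 5.0% | 7.2% | 13.1% |
| Part 2, 3 cohorts (9 v 9) | 5.0% | 6.7% | 11.3% |
| Part 1, 5 cohorts (6 v 10) | 5.0% | 6.5% | 10.5% |

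**Step 3: check.** The formulas treat the error variance as scaled chi-square. Simulation with 60,000 runs per setting agreed: 7.1% and 12.7% for four Part 2 cohorts, 6.7% and 10.3% for Part 1, and t-test power of 75.0%, 72.3% and 69.6% at τ = 0, 1/3 and 0.5. The model with a cohort term rejected in 4.8% to 5.2% of null runs.

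**Step 4: why the same term is not free for a single dose.** Each dose sits in one cohort, so adjusting for cohort reduces a dose contrast to 9 v 3. Its standard error is √(1/9 + 1/3) = 0.667, against √(1/9 + 1/12) = 0.441 with pooled placebo and τ = 0. An effect of 1.30 SD, which has 80% power at 9 v 12, has about 48% at 9 v 3 (40 error df).

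**The case against.** **The planned test is not confounded in general.** A reader might infer that the t-test tests a joint hypothesis of no drug effect and no cohort difference. With the same ratio in every cohort that is wrong for all active against all placebo: Step 1 shows rejection at or below 5%. It fits only the one-cohort comparison, which the cohort-size argument in Section 14.1 suggests but Section 14.4 does not state. This part of the objection stands.

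**The size rests on an unknown.** The documents give no between-cohort variance, the study is single-center, and nothing says samples are assayed in cohort batches. At a 5% variance share the single-cohort rate is only 6.2% to 6.8%. If baseline-corrected values were tested, shifts common to pre-dose and post-dose samples would drop out. This stands too, although Section 14.4 keeps changes from baseline descriptive.

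**The analysis is exploratory.** Section 14.4 makes it optional (the Synopsis words it more firmly), the RAP may add detail, and the hematology-based dose cap in Section 6.4 uses no statistical test. That limits the importance. It does not argue against a term that costs almost nothing.

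**Requiring confirmation against the cohort's own placebo would be costly.** Step 4 bears this out. A rule that no Treg conclusion may rest on pooled placebo alone is not supported.

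**Conclusion.** The point holds in a limited form. Section 14.4 omits the factor within which the trial randomizes.

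- For all active against all placebo, the t-test is valid but conservative. It loses about 2 points of power at a between-cohort SD of one third of the within-cohort SD, and about 6 points at one half (four Part 2 cohorts, 0.9 SD effect).
- For one cohort against pooled placebo, if that is what is meant, the false-positive rate at ratios of 0.25 and 0.5 is about 7% and 13% in Part 2 with four cohorts, and about 6.5% and 10.5% in Part 1 with five.

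These figures assume normal outcomes, complete cohorts, two-sided 5% tests and the stated between-cohort SDs. If cohorts do not differ, there is no harm. The documents do not show that cohorts will differ, so they do not support saying that the planned test will give false Treg findings.

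**What to change.** 1. In Section 14.4 or the RAP, before unblinding, replace the active-versus-placebo t-test within each part by a linear model with treatment and cohort as fixed factors. If the non-parametric option is used, stratify the rank test by cohort (van Elteren).
2. State which active group is compared with which placebo group.
3. For any comparison of a single dose with pooled placebo, state that most of the controls are non-concurrent. Show beside it the difference from that cohort's own placebo subjects, as a descriptive sensitivity check and not as a condition for drawing a conclusion.

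Cost: a few lines of text and 2 to 4 degrees of freedom (K − 1 for three to five cohorts). There is no measurable loss of power if cohorts do not differ (75% either way in Step 1). No change to sample size, sampling or randomization is needed.
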